2.9 Safety analyses

Safety measurements include duration of exposure, vital signs and adverse events. All safety endpoints will be summarized using the Safety Set. Patients will be analyzed according to treatment received. No imputation will be carried out for missing data.

2.9.1 Adverse events (AEs)

All information obtained on AEs will be displayed by patient. Summary tables for AEs will summarize only on-treatment events, with a start date during the on-treatment period (see Section 2.1.1) for definition of on-treatment period).

The count of treatment-emergent AEs, number (and percentage) of patients with treatment-emergent AEs (defined as events started after the first dose of study treatment or events present prior to start of study treatment but increased in severity based on PT) will be summarized in the following ways:

- By primary SOC and PT.
- By primary SOC, PT and maximum severity.

Separate summaries will be provided for study treatment related AEs, procedure related, death, SAEs and other significant AEs action taken leading to study treatment interruption & treatment withdrawn.

Adverse events will be summarized by presenting, the number and percentage of patients having any AE, having an AE in each primary SOC and having each individual AE (PT). Summaries will also be presented for AEs by severity. Summaries for AE will be presented for study treatment and procedure related to AEs. If a patient reported more than one AE with the same PT, the AE with the greatest severity will be presented. System organ classes will be presented in alphabetical order, PTs will be sorted within SOC in descending frequency of AEs. If a patients reported more than one AE within the same primary SOC, the patient will be counted only once with the greatest severity at the SOC level, where applicable. The AE will be presented in separate sections of ocular and non-ocular. For ocular then it will be presented by any eye, study eye and fellow eye.

For occurrence, the presence of at least one SAE / SAE suspected to be related to study treatment / non SAE has to be checked in a block e.g., among AEs in a \leq 1 day gap block, if at least one SAE is occurring, then one occurrence is calculated for that SAE.

The number of deaths resulting from SAEs suspected to be related to study treatment and SAEs irrespective of study treatment relationship will be provided by SOC and PT.

In addition, all treatment emergent AEs will also be listed.

The by-patients listing will include: SOC/PT/Verbatim term, start date, end date, severity, relationship to study treatment and procedures, whether or not it is a SAE, action taken with study treatment and outcome. Duration will be calculated as (end date – start date + 1) and for ongoing AE (last visit date – start date + 1) by ocular and non-ocular. For ocular then it will be presented by any eye, study eye and fellow eye.

A summary of action taken with number and percentage of patients will presented with dose increased, no dose change, dose reduced, treatment interrupted, drug withdrawn, not applicable and unknown.

2.9.1.1 Adverse events of special interest / grouping of AEs

The number (%) of patients with AESIs will be summarized by standardized MedDRA query and PT. Listing will also be provided.

Case Retrieval Sheet (CRS) with the exact composition of the AE groupings is to be used to map reported AEs to the AESI groupings. This file may be updated (i.e.live document) based on review of accumulating trial data, and therefore the groupings are also subject to potential change. The most up-to-date version of the CRS will be used at the time of the analysis.

The number and percentage of patients having any AESI, AESI by SOC (confirmed by SRC) and PT will be presented.

The number and percentage of patients for AESI type along with incidence rate per patient and per 1000 injection will be provided. Incidence rate per patient is defined as number of patients in AESI type/total number of patients in safety analysis set and incidence rate per 1000 injection is define as (number of occurrence of AESI type/total number of injections)*1000.

The number and type of AESI will be plotted according to the time after last brolucizumab injection and time since first brolucizumab injection.

Summary statistics for change from baseline in BCVA after end date of AESI will be provided for each AESI type and change from baseline in BCVA will be plotted overall and for each type of AESI.

Patients demographics, baseline characteristics and medical history will be provided for AESI patient with safety set.

2.9.2 **Deaths**

A separate summary of deaths including on-treatment and post-treatment deaths will be provided.

All deaths in the clinical database will be listed with the investigator-reported principal cause. Deaths occurring after the first dose of study treatment until 30 days after the date of last treatment will be summarized. In addition, deaths occurring after the first dose of study treatment until the date of last treatment will also be summarized.

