Patients will receive 3 initial doses every 4 weeks (Day 1, Week 4 and Week 8) (loading phase), which should be at least 21 days apart, followed by treatment q12w with the possibility of adjusting to treatment q8w based on disease activity. Disease activity will be assessed based on investigator's judgment of visual acuity and anatomical parameters as provided in the guidance to the investigators, e.g. decrease of visual acuity and/or other signs of the disease (e.g. intraretinal fluid (IRF), subretinal fluid (SRF), sub-retinal pigmented epithelium (sub-RPE) fluid, retinal hemorrhage, central retinal thickness (CRT) increase, etc.). Disease activity will be assessed during the first q12w interval at Week 16. If no disease activity is observed by the investigator in the study eye, disease activity will be assessed every 12 weeks (at Week 20, Week 32 and Week 44). If disease activity is observed by the investigator in the study eye at any of these visits, the study treatment will be adjusted by the investigator to a q8w treatment regimen and will remain on this regimen until Week 40/Week 44 (see [Section 6.7.2](#)). Patients who require study treatment every 4 weeks after the initiation phase will be discontinued from further study treatment at the next visit.

The mandatory study visits during the treatment phase are Day 1, Week 4 and Week 8 (assessment of CNV lesion evolution during initiation phase), Week 12 (primary endpoint), Week 16 (first time to reach disease activity criteria and first possible treatment) and Week 48 (last efficacy assessment) visits. The timing of the interim visits between Week 16 and Week 48 will depend on the patient's injection regimen, i.e. q12w or q8w. No visits are planned between the injection visits (see [Section 6.7.2](#)).

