### q12w/q8w treatment phase

The mandatory visit at Week 12 will be performed to evaluate the primary endpoint of the study. No treatment will be administered at Week 12; the next visit will take place at Week 16. Disease activity will be assessed at Week 12 for endpoint assessment purposes.

The q12w/q8w treatment phase starts at Week 16 and is defined as follows:

- Following Week 8, treatment intervals will be either 8 weeks or 12 weeks. A patient must be discontinued from further study treatment if treatment is required more frequently, i.e., every 4 weeks.
- The first assessment of disease activity during this phase will be performed at the Week 16 visit by the investigator.
- Based on investigator's judgment of visual and/or anatomic outcomes, the treatment can be adjusted by the investigator to a q8w treatment regimen if there is disease activity as

provided in the guidance to the investigators, e.g. decrease of visual acuity and/or other signs of the disease (e.g. IRF, SRF, sub-RPE fluid, retinal hemorrhage, CRT increase, etc.).

- The disease activity assessment is performed at each subsequent visit by the investigator.
- If disease activity is identified, the patient will be reassigned to receive injections q8w thereafter up to Week 40/Week 44.
- Regardless of treatment administration, Week 16 and Week 48 visits are mandatory.
- The timing of the interim visits between Week 16 and Week 48 will depend on the patient's injection regimen, i.e. q12w or q8w.
- No visits are planned between the injection visits.
- The last potential study treatment may be administered at the Week 40 visit or at the Week 44 visit according to the patient's treatment regimen.
- A disease activity assessment will also be performed at the Week 48/EOS visit; however, no study treatment will be administered.

The different types of visits occurring through the study are summarized in [Table 6-3](#) with a description of when disease activity assessment and treatment take place.

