 Intraocular pressure (IOP) will be assessed in the study eye, pre-dose and post-dose at every injection. The same method of tonometry has to be used through the whole study. Close monitoring of IOP should be performed by the investigator for any non-transient elevation in IOP ( $\geq 25$  mmHg). Intravitreal injection is not recommended unless normalization of the IOP has been achieved. Post-dose IOP should be assessed within 60 minutes after injection and if  $\geq 25$  mmHg, assessment should be repeated until back to normal. Monitoring of the optic nerve head perfusion after injection may be appropriate, at the discretion of the investigator. Results of these procedures will be recorded as appropriate in the source documents and if the findings constitute an AE, it should be recorded in the eCRF.

 Additional ophthalmic examinations and images will be performed in case of any signs of intraocular inflammation (IOI), retinal vasculitis, and/or retinal vascular occlusion.

 A telephone follow-up on safety should be performed one week after the first injection (a window for the phone call is +7 days). From the second injection onwards, similar phone calls should be made at investigator's discretion per local practice.

 The week 48 EOS assessments only apply to patients who completed the study per protocol. The assessments are not required for patients who have undergone ETD assessments and continued in the study without study treatment.

 ETD: Early treatment discontinuation applies to patients who discontinue early from study treatment and continue in the study. The assessments should be performed 4 weeks after the last injection of study drug. This can occur at any time point.

 For patients who continue in the study after ETD and up to Week 48 (end of study) while patient is on standard of care. Additional safety assessments and imaging can also be performed if required, as per investigators discretion. In addition, after ETD, subjects are not required to attend the mandatory visits at Week 12 and Week 48. The last visit should be at week 48. This can occur at any time point.

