### **12.5.2 Safety endpoints**

For all safety analyses, the Safety Set will be used.

The secondary safety endpoint of this study is as follows:

- Incidence of AEs (serious and non serious) reported in patients treated with brolocizumab.

Safety summaries (tables, figures) include only data from the on-treatment period with the exception of Baseline data, which will also be summarized where appropriate (e.g. change from Baseline summaries). In addition, a separate summary for death including on treatment and post treatment deaths will be provided. In particular, summary tables for adverse events of special interest (AESIs) will summarize only on-treatment events, with a start date during the on-treatment period (treatment-emergent AEs).

The on-treatment period lasts from the date of first administration of IVT injection of study treatment to 30 days after the date of the last actual administration of IVT injection of study treatment.

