Change from Baseline: The difference of measure between post-baseline and Baseline is called change from Baseline.

Percent change from Baseline: The percent change from Baseline will be calculated as below: ((post-baseline value – Baseline value) /Baseline value)*100.

On-treatment period: The on-treatment period lasts from the date of first administration of study treatment to 28 days after the date of the last actual administration of any study treatment.

Treatment duration: The maximum planned duration of treatment for each patient is 40 to 44 weeks in accordance with the designated treatment regimen. Discontinuation of study treatment for a patient occurs when study treatment is stopped earlier than the protocol planned duration and can be initiated by either the patient or the investigator.

Treatment discontinuation: When patients discontinue study treatment but continue in the study, the efficacy data will be used at the time the patient stopped study treatment.

Dry retina: Absence of fluid (IRF/SRF/sub-RPE) will be considered as dry retina.

Event for maintenance q12w interval: In case the investigator selects q12w interval for a patient and the patient maintains the q12w interval until the first q8w interval has started then this will be considered as an event. In case the investigator maintains q12w interval (does not select q8w interval at any time in study) until EOS or patients got early discontinuation from study then patients will be considered as censored.

Event for no disease activity: When patients will be with no disease status as per investigator decision after last dose in initiation phase then the patients will consider as event for disease activity. If patients with active disease status or early discontinue then patients will be considered as censored for disease activity.

Event for dry retina: When patients have absence of fluid then it will be considered as an event of dry retina. If patients have a presence of fluid before/at EOS or early discontinuation then will be censored.

Maximum duration of dry retina: The longest consecutive interval of dryness will be considered as maximum duration of dryness. This duration will be obtained from end date of dryness and start date of dryness for longest interval. If subjects obtain dryness at end of study then duration will be obtained from end of treatment.

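### AESI counts plotted by time after the last injection need time at risk, because the dosing schedule alone makes later bins smaller

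*SAP*

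**What the plan says.** SAP Addendum 1.0, section 2.9.1.1, plans these displays of AESI timing: "The number and type of AESI will be plotted according to the time after last brolucizumab injection and time since first brolucizumab injection". It mentions no patients, injections or person-time at risk for them. The section's denominators are the number of patients in the safety set and the total number of injections: "number of occurrence of AESI type/total number of injections)*1000". Neither is divided by time.

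The schedule determines how long each injection is followed. The three loading doses are at Day 1, Week 4 and Week 8. Thereafter, under Protocol section 6.7.2, "Following Week 8, treatment intervals will be either 8 weeks or 12 weeks". Protocol section 3 places the final assessment at Week 48, which is 4 weeks after a last dose at Week 44 or 8 weeks after a last dose at Week 40.

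The analysis window is not settled. Protocol section 12.5.2 says "Safety summaries (tables, figures) include only data from the on-treatment period", and that period runs "to 30 days after the date of the last actual administration of IVT injection of study treatment". SAP section 2.1.1 ends it differently: "to 28 days after the date of the last actual administration of any study treatment". SAP section 2.9.1 applies the restriction to AE summary tables and says nothing about figures. Two analyses are planned, at Week 12 and after Week 48 (Protocol section 12, SAP section 2.14). Section 2.9.1.1 does not say which one the plots serve.

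**The concern.** A count against time since the last injection combines how often events occur with how many injections are still being followed. Each new injection resets the clock, so the number followed falls in steps at 28 and 56 days. A reader who sees fewer events in the second and third months will naturally conclude that risk fades with time since dosing, even if it does not.

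This matters because intraocular inflammation, retinal vasculitis and retinal vascular occlusion led to Protocol Amendments 2 and 3 and part of Amendment 4. These plots are the only display of onset timing that the SAP text specifies for them.

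**Working it through.** **Plan's own figure.** The documents give no time at risk for AESI, so there is nothing to reproduce on this point. The planned N is used only for scale, and it checks: (1.96 × 35 / 5)² = 188.2, rounded up to 189; 189 / 0.90 = 210.

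**Inputs.** Nominal injection weeks come from Protocol sections 3 and 6.7.2, with follow-up to Week 48. Patients are assumed to complete the study on nominal dates. Follow-up of an injection is the gap to the next injection, or to Week 48.

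| Pattern | Injection weeks | Gaps (weeks) | Weeks in days 0-28 / 29-56 / 57-84 | Injections followed past day 28 | Past day 56 |
|---|---|---|---|---|---|
| q12w throughout | 0, 4, 8, 20, 32, 44 | 4, 4, 12, 12, 12, 4 | 24 / 12 / 12 | 3 of 6 (50%) | 3 of 6 (50%) |
| q8w from Week 16 | 0, 4, 8, 16, 24, 32, 40 | 4, 4, 8, 8, 8, 8, 8 | 28 / 20 / 0 | 5 of 7 (71%) | 0 of 7 (0%) |
| q8w from Week 20 | 0, 4, 8, 20, 28, 36, 44 | 4, 4, 12, 8, 8, 8, 4 | 28 / 16 / 4 | 4 of 7 (57%) | 1 of 7 (14%) |
| q8w from Week 32 | 0, 4, 8, 20, 32, 40 | 4, 4, 12, 12, 8, 8 | 24 / 16 / 8 | 4 of 6 (67%) | 2 of 6 (33%) |

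**Effect under a constant hazard.** Expected counts are proportional to patient-time. The ratio of days 57-84 to days 0-28 is 12/24 = 50% for q12w throughout and 0/28 = 0% for q8w from Week 16. Any mix of patterns lies between these limits.

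**Assumed mixes** (q12w / switch at Week 16 / Week 20 / Week 32):
- 60/25/10/5%. Days 0-28: 0.60×24 + 0.25×28 + 0.10×28 + 0.05×24 = 25.4 weeks. Days 29-56: 14.6. Days 57-84: 0.60×12 + 0.10×4 + 0.05×8 = 8.0. Shares of 48 weeks are 53/30/17%, and the ratio is 8.0/25.4 = 31%.
- 40/40/15/5%. The same sums give 26.2, 16.0 and 5.8 weeks. Shares are 55/33/12%, and the ratio is 5.8/26.2 = 22%.

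**Effect of the on-treatment window.** A cut 28 days after the last dose shortens only the final 8-week gap of patients last dosed at Week 40. For q8w from Week 16, patient-time becomes 28/16/0 of 44 weeks, or 64/36/0%. Injections followed past day 28 become 4 of 7 (57%) for that pattern and 3 of 6 (50%) for a Week 32 switch. Days 0-28 and 57-84 do not change, so the 22-31% stands.

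**Week 12 cut.** The gaps are 4, 4 and 4 weeks, so none of the three injections is followed past day 28 on nominal dates.

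**Time since first injection.** A completer contributes all 336 days, or 280 + 28 = 308 days if last dosed at Week 40 and cut at 28 days. Dosing gaps do not thin this axis.

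**Scale of the counts.** Protocol section 4.5 quotes inflammation-related event rates of 3.2% in men and 5.3% in women from the two pivotal trials. If these carried over (an assumption), 210 × 0.032 = 6.7 to 210 × 0.053 = 11.1 patients would be affected. Counting one event each, days 57-84 would expect 6.7 × 0.12 = 0.8 to 11.1 × 0.17 = 1.9 events. Under a flat hazard the Poisson chance of an empty third-month bin is then e^-0.8 = 45% down to e^-1.9 = 15%.

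**The case against.** The best defence is that these are supplementary descriptive plots in a single-arm study. The stated safety endpoint is AE incidence, and time to onset is not an endpoint. The same section already provides percentages, two incidence rates and a listing. With so few events expected, late-bin rates will be unstable. Figure layouts are left to the TFL shells, which are not in the documents and might carry a row of numbers at risk. Much of this stands, and it limits the importance of the point. It does not remove it: the SAP text specifies counts, its denominators are not split by time, and sparse data make an empty late bin easier to misread.

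Three stronger readings are tempting, and the documents support none of them.

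- A reader might infer that few injections are followed beyond 28 days. By schedule 50-71% are, and at least 50% even with the 28-day cut. That window runs from the last dose, so it truncates one injection per patient.
- A reader might infer that both axes are distorted alike. Completers are observed to Week 48, and Protocol section 9.1.1 collects AEs to Week 48 after early discontinuation. Only dropout and any end-of-treatment cut thin the time-since-first axis.
- A reader might infer that wider visit spacing produces the same artefact. Protocol section 3 does say "No visits are planned between the injection visits", and Table 8-1 adds "From the second injection onwards, similar phone calls should be made at investigator's discretion per local practice". But this concerns ascertainment, not time at risk, and rates per patient-day would not correct it. Patients are told to report symptoms between visits (Protocol sections 8.4.3 and 10). Planned contacts in Weeks 16-48 also vary by pattern: four for most, five after a Week 20 switch (Weeks 20, 28, 36, 44 and 48).

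**Conclusion.** The point holds for the plot by time after the last injection. Without time at risk, its later bins are lower by design: a flat hazard would give days 57-84 about 22-31% as many events as days 0-28. That range rests on completers dosed on nominal dates and on assumed mixes with 40-60% staying on q12w. With no assumption about the mix, the limits are 0% and 50%. Visit windows of ±7 days and dropout would shift the figures modestly.

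Nothing here shows that the hazard is constant, only that the planned display cannot distinguish a constant hazard from a falling one. No primary or secondary endpoint is affected. This is a cheap improvement.

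**What to change.** Keep both number-and-type plots and add to SAP section 2.9.1.1:

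- Under the time-after-last-injection plot, print injections and patient-days at risk for days 0-28, 29-56, 57-84 and beyond 84. Give events per patient-day in each bin with exact Poisson intervals. The last bin is needed for discontinued patients followed to Week 48, if their later events are plotted.
- Under the time-since-first-injection plot, print patients at risk.
- State which data cut the plots use and whether events after the on-treatment window are included.
- Reconcile the 28-day window in SAP section 2.1.1 with the 30-day window in Protocol section 12.5.2.

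The cost is SAP wording and a small programming task on injection, visit and event dates already collected. The downside is imprecision in later bins, which the intervals will show. Rates also leave one limit: days 57-84 contain only 12-week intervals, hence mainly patients not judged active at Week 16. A figure note should say that the bins compare different patients.
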